4.2 SCIENTIFIC RATIONALE FOR STUDY DESIGN

The rationale for this study is to determine if timing of local anesthetic infiltration impacts overall pain score or narcotic usage. Although use of local anesthetic has been shown to reduce pain, there is no literature in gynecologic surgery regarding the timing of infiltration and its impact, if any, on pain.

4.3 JUSTIFICATION FOR DOSE

Standard dose used.

4.4 END OF STUDY DEFINITION

A participant is considered to have completed the study if the patient has completed all phases of the study including the narcotic pain diary and brief pain inventory questionnaire at the first postoperative visit at approximately two weeks.

5 STUDY POPULATION

5.1 INCLUSION CRITERIA

- Females 18+ years old who are undergoing robotic/laparoscopic assisted sacrocolpopexy
 - With/without hysterectomy
 - With/without unilateral/bilateral salpingectomy
 - With/without unilateral/bilateral oophorectomy
 - With/without midurethral sling
 - With/without anterior/posterior vaginal repair
- English or Spanish speaking
- Weight \geq 120 lbs

5.2 EXCLUSION CRITERIA

- Females < 18 years old
- Chronic pelvic pain/chronic pain syndromes
- Fibromyalgia
- Pregnant or breastfeeding patients
- Concomitant procedure for hernia repair or rectal prolapse repair
- Undergoing primary vaginal prolapse surgery
- Contraindications to taking the following medications: Bupivacaine
- Patients who weight is < 120lb
- Hypersensitivity to bupivacaine hydrochloride, amide-type local anesthetics, or any component of the formulation
- Pudendal or spinal nerve block given during surgery

5.3 LIFESTYLE CONSIDERATIONS

Our standard post-operative instructions will remain.

5.4 SCREEN FAILURES

Screen failures are defined as participants who consent to participate in the clinical trial but are not subsequently randomly assigned to the study intervention or entered in the study. A minimal set of screen failure information is required to ensure transparent reporting of screen failure participants, to meet the Consolidated Standards of Reporting Trials (CONSORT) publishing requirements and to respond to queries from regulatory authorities. Minimal information includes demography, screen failure details, eligibility criteria, and any serious adverse event (SAE).

5.5 STRATEGIES FOR RECRUITMENT AND RETENTION

- Patients will be screened and recruited from the Urogynecology outpatient clinic who are scheduled to undergo surgical management to correct their prolapse.

- At the visit in which the patient is considering surgical management for prolapse, all questions will be answered and she may be given a printed pamphlet that describes and details the study
- At the preoperative visit, if the patient has decided to undergo the robotic/laparoscopic-assisted sacrocolpopexy, patient will again have an opportunity to ask questions of the study, counseled on the risks/benefits of its participation and informed consent will be obtained
 - If she is undecided about joining the study, but is planning to undergo robotic/laparoscopic-assisted sacrocolpopexy, then she will be given additional time and called prior to surgery to answer any additional questions about the study and evaluate participation
 - If the patient did not sign on the preoperative visit, then she will be given another opportunity to sign the consent form on the day of surgery in the preoperative area and answer any further additional questions
- Email and phone call reminders to patients for postoperative appointment date and to fill out narcotic diary
- No vulnerable populations will be targeted for recruitment
- No incentives will be provided

6 STUDY INTERVENTION

6.1 STUDY INTERVENTION(S) ADMINISTRATION

6.1.1 STUDY INTERVENTION DESCRIPTION

Study Drug

- 0.25% Bupivacaine
 - Mechanism of action: blocks both the initiation and conduction of nerve impulses by decreasing the neuronal membranes permeability to sodium ions, which results in inhibition of depolarization with resultant blockade of conduction

6.1.2 DOSING AND ADMINISTRATION

Study Drug

- Anesthesia team will be notified the total dose of medication being injected prior to case start
- Anesthesia team will be notified when the study drug is being injected
- 4-5 mL of 0.25% Bupivacaine given subcutaneously at each of the injection sites (total of 5 incisions)

6.2 PREPARATION/HANDLING/STORAGE/ACCOUNTABILITY

6.2.1 ACQUISITION AND ACCOUNTABILITY

- Study drug will be obtained from the hospital pharmacy

- Any expired local anesthetic will not be used at the time of surgery, as per standard protocol
- Any remaining medication will be disposed at the end of procedure, as per standard protocol
- Study intervention will be emailed to investigator before surgery

6.2.2 FORMULATION, APPEARANCE, PACKAGING, AND LABELING

0.25% Bupivacaine is already pre-packaged and comes with the label of Marcaine (Bupivacaine) 0.25% directly to the hospital pharmacy. This drug is then pre-ordered and brought to the operating room where the designated amount will be drawn up into sterile syringes.

6.2.3 PRODUCT STORAGE AND STABILITY

- Product will be obtained from the hospital pharmacy where the medication is stored at room temperature
- In the operating room, the medication seal will be broken after confirming expiration date has not passed
- The medication will be stored at room temperature in the operating room until time for administration

6.2.4 PREPARATION

- The medication will be provided by hospital pharmacy
- No special dilution or mixing required
- Medication will be drawn up in sterile syringes by operating room staff

6.3 MEASURES TO MINIMIZE BIAS: RANDOMIZATION AND BLINDING

- Patient-blinded study
- Multi-site study
- The surgeon at the time of intervention will not be blinded as to which arm the patient belongs
- Randomization will be performed using 1:1 randomization, permuted blocks

Randomization will be accomplished using the Biostatistics Randomization Management System according to hospital site.

6.4 STUDY INTERVENTION COMPLIANCE

Adherence to the protocol will be confirmed and assessed by speaking directly with the primary surgeon prior to the procedure and at the end of procedure. The surgeon will be informed of each participant study allocation. The surgeons have been informed and continued to review how to inject the medication depending on the patient groups during monthly research meetings per discussion and teachings. The patient's Likert-pain scale will be assessed 18-24 hours after surgery. Documents that are mandatory to complete by the patient will be a participant drug log, in which the number of narcotic tablets used and pain score will be recorded daily by the patient.

6.5 CONCOMITANT THERAPY

Patients who participate in the study will receive the following standardized pain regimen:

- General anesthesia will be given as per standard protocol
- Preoperative pain medication will be ordered for each patient as per standard enhanced recovery protocol.
- Postoperative pain medication will be ordered for each patient as per standard enhanced recovery protocol.
- Discharge medications will be ordered for each patient as per standard enhanced recovery protocol.

6.5.1 RESCUE MEDICINE

Not applicable

7 STUDY INTERVENTION DISCONTINUATION AND PARTICIPANT DISCONTINUATION/WITHDRAWAL

7.1 DISCONTINUATION OF STUDY INTERVENTION

If the first ten patients do not tolerate the study medication, then we will evaluate which adverse reaction the patients experience and as to which arm they were randomized. We will also evaluate at which time point they experienced an adverse reaction and if it was to a preoperative/postoperative medication or if it was to the study drug. Pending the determination of these, we will halt recruitment. It is possible for a patient to discontinue participating in the study after surgery, but not during surgery.

7.2 PARTICIPANT DISCONTINUATION/WITHDRAWAL FROM THE STUDY

An investigator may discontinue or withdraw a participant from the study for the following reasons:

- Pregnancy
- If any clinical adverse event (AE), laboratory abnormality, or other medical condition or situation occurs such that continued participation in the study would not be in the best interest of the participant
- If the participant meets an exclusion criterion (either newly developed or not previously recognized) that precludes further study participation

The reason for participant discontinuation or withdrawal from the study will be recorded on the Case Report Form (CRF). Subjects who sign the informed consent form and are randomized but do not receive

the study intervention may be replaced. Subjects who sign the informed consent form, and are randomized and receive the study intervention, and subsequently withdraw, or are withdrawn or discontinued from the study, will not be replaced.

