4 STUDY DESIGN

4.1 OVERALL DESIGN

- Central Objective To examine patients reported pain levels or narcotic usage between pre-incision versus post-incision subcutaneous infiltration of 4-5mL 0.25% Bupivacaine after a robotic/laparoscopic-assisted sacrocolpopexy.

Research Plan:

- Randomized, controlled, single-blinded study

Setting of the study:

- Operating room of patients undergoing robotic/laparoscopic sacrocolpopexy

Participants:

- Patients aged 18 years old and above who are scheduled to undergo robotic/laparoscopic-assisted sacrocolpopexy (with or without hysterectomy and with or without midurethral sling)

Randomization Scheme

- Randomization will be accomplished using the Biostatistics Randomization Management System
- 1:1 Randomization, permuted blocks
- Subjects will be randomized using a computer generated table into one of two groups:
 - Arm one: subcutaneous infiltration pre-incision
 - Arm two: subcutaneous infiltration post-incision
- Surgeons will be notified by e-mail of their patient allocation on day of surgery

Pre-surgery

- Consent will be obtained and the patient will be given a Brief Pain Inventory Questionnaire to complete. The Brief Pain Inventory Questionnaire is a validated medical questionnaire to measure pain. The questionnaire measures the patient's pain intensity and the amount of interference the pain has on their being able to function in their daily living.
- Intervention or experimental aspect of the study
 - General anesthesia will be given as per standard protocol
 - Preoperative pain medication will be ordered for each patient as per standard enhanced recovery protocol
 - Operative Time: Generally total of 180 – 300 minutes
 - Total dose of 0.25% Bupivacaine injection:
 - 8-10 mm incisions x 5 incisions = 20-25 mL (4-5 mL each)
 - 20-25mL of 0.25% Bupivacaine distributed over 5 trocar sites (4-5mL per incision)
 - Skin closure: subcutaneous closure with monofilament absorbable suture with 4-0 absorbable suture and fascia closure of the umbilical port site with #0 delayed absorbable suture and skin closure with 4-0 absorbable suture

- Pre-incision arm: Marcaine (bupivacaine) injected in the umbilical port site subcutaneously, while in the other 4 sites injection under direct visualization
- Post-incision arm: local anesthetic infiltrated subcutaneously at the end of the procedure after trocar removal and after skin closure with suture

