9.3 POPULATIONS FOR ANALYSES

Intention to Treat (ITT) and Per Protocol (PP) analysis data sets:

The ITT dataset will consist of all randomized patients. If applicable, a modified ITT (mITT) dataset will consist of all ITT patients who receive the actual assigned timing of infiltration. We expect no protocol violation based on the design of the study. The safety population will consist of all mITT patients.

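### Replacement (7.2) and mITT membership (9.3) both depend on receipt of an injection that the two arms get at opposite ends of surgery, so a withheld late injection is handled differently by arm

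*Combined protocol and SAP*

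**What the plan says.** Section 7.2 splits randomised patients by whether they were injected. For those who were not: "Subjects who sign the informed consent form and are randomized but do not receive" it "the study intervention may be replaced". For those who were injected "and subsequently withdraw, or are withdrawn or discontinued from the study, will not be replaced". No criteria are given for using the discretion, and nothing says which arm a replacement enters.

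Section 4.1 places the injections at opposite ends of the operation. Arm one is infiltrated before incision. For arm two the text is: "Post-incision arm: local anesthetic infiltrated subcutaneously at the end of the procedure after trocar removal and after skin closure with suture". The same section gives "Operative Time: Generally total of 180 – 300 minutes".

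Section 9.3 states that "The ITT dataset will consist of all randomized patients". It then defines an mITT set limited to patients who got their assigned timing, and makes the safety population the same as mITT. Section 9.4.2 specifies the primary t-test and the ±1 equivalence rule but does not say which set they use. It also gives no method for missing day-1 scores.

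Section 6.3 adds that "The surgeon at the time of intervention will not be blinded as to which arm the patient belongs".

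**The concern.** Replacement and analysis-set rules should not depend on something that happens after randomisation at a different time in each arm. Here they do. From first incision to skin closure, an injected pre-incision patient has already met the receipt condition, while a post-incision patient has not. If something during the operation leads to the late injection being withheld, only the post-incision patient becomes replaceable and leaves mITT.

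If such patients differ in day-1 pain, the two arms are no longer selected in the same way. That would affect the primary comparison at 18–24 hours and the secondary endpoints. A larger sample would not remove the effect. The surgeon who gives or omits the late injection knows the allocation, so the omission could itself depend on the arm.

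**Working it through.** **1. The plan's own figure.** Inputs from 9.2: difference 1, SD 2, two-sided alpha 0.05, power 0.80, 1:1 allocation, drop-out 0. The two-sample t-test needs 63.77 per arm, rounded up to 64 (power 80.1%). The stated 64 per arm is reproduced, and this point does not dispute it.

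**2. One event traced through both arms.** Take an event between first incision and closure after which no further study injection is given.

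| | Pre-incision arm | Post-incision arm |
|---|---|---|
| Injected before the event? | Yes | No |
| Replaceable under 7.2? | No | Yes, at discretion |
| In ITT (9.3)? | Yes | Yes |
| In mITT and safety sets (9.3)? | Yes | No |

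The arms differ in the second and fourth rows. The window is roughly the operative time of 3–5 hours; this gap is inferred from 4.1, not stated there.

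**3. What the documents offer as triggers.** Section 8.4.4 stops therapy for a severe abnormal heart rhythm at any study visit, and surgery is Visit 2. A pudendal or spinal block during surgery is an exclusion criterion (5.2), and 7.2 allows withdrawal for a newly developed one. Section 8.1 checks after surgery that the assigned infiltration was given, so omission is recognised as possible.

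**4. When bias follows.** Let a proportion e of patients have such an event, and let their mean day-1 score be D points higher than the mean m of the rest.
- Mean of a full arm: (1 − e)·m + e·(m + D) = m + e·D.
- Mean of an arm without these patients: m.
- Bias (pre minus post) if they are analysed in the pre-incision arm and missing from the post-incision arm: e·D.

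This requires the post-incision scores to be lost, or mITT to be the set used. Adding a replacement changes only the number analysed, not e·D.

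**5. Size.** Neither e nor D is in the documents; both are assumed.

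| e | Expected patients per 64 | Bias, D = 1 | D = 2 | D = 3 |
|---|---|---|---|---|
| 1% | 0.6 | 0.01 | 0.02 | 0.03 |
| 2% | 1.3 | 0.02 | 0.04 | 0.06 |
| 5% | 3.2 | 0.05 | 0.10 | 0.15 |
| 10% | 6.4 | 0.10 | 0.20 | 0.30 |

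**6. Against the equivalence rule.** SE = 2 × √(2/64) = 0.354. The 95% half-width is 1.979 × 0.354 = 0.70. The interval lies within ±1 only if the observed difference is within 1 − 0.70 = 0.30 of zero. With truly equal arms and SD 2, the chance of that is:

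| Bias | Chance of concluding equivalence |
|---|---|
| 0 | 60% |
| 0.04 | 60% |
| 0.10 | 59% |
| 0.15 | 56% |
| 0.30 | 46% |

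**7. Effect on power through numbers alone.** Suppose events are lost in the pre-incision arm and fully replaced in the other. Power for a 1-point difference falls from 80.1% to 79.1% at e = 5% and to 78.0% at e = 10%. Loss of numbers is a minor matter; selection is the issue.

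**The case against.** The strongest reply is that replacement removes nobody. Section 9.3 keeps every randomised patient in ITT, so a strict ITT analysis with all day-1 scores collected carries none of this bias. That stands. It protects the result only if ITT is the primary set and the scores exist, and 9.4.2 secures neither.

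A reader might go further than the documents allow in five ways.
- **That nothing keeps these patients in follow-up.** Section 8.4.4 follows severe rhythm events to end of study and severe allergic reactions for two weeks. Both periods cover the 18–24 hour score. The gap is for other reasons for a withheld injection.
- **That non-receipt can occur in one arm only.** Surgery cancelled after randomisation would leave a pre-incision patient uninjected too. Section 4.1 also describes her umbilical site separately from the other four, so partial receipt is conceivable. The asymmetry concerns events after she has been injected.
- **That the pre-incision counterpart is certain to be analysed.** Section 7.2 says she is not replaced if withdrawn, not that she stays. If she too is withdrawn and unscored, the contrast shrinks or disappears.
- **That the bias is known to favour post-incision infiltration.** That needs D above zero, and no figure in the documents supports it.
- **That complicated cases are refilled within the same arm.** Replacement is optional, and its arm is not stated.

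Nor does every event qualify. A reaction to bupivacaine itself cannot precede injection in the post-incision arm, and conversion to open surgery is not discussed. Section 9.3 expects no protocol violations. Section 7.1 bars a patient from discontinuing during surgery, although 7.2 sets no such limit on investigator withdrawal and its replacement rule turns on receipt.

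**Conclusion.** The point holds as a flaw in the rules, not as a demonstrated bias. Sections 7.2 and 9.3 make replaceability and mITT membership depend on an event whose timing differs by arm, and no common cut-off is set. The result is biased only if the day-1 scores of non-injected patients are missing or mITT carries the primary comparison; the plan leaves both open.

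Across the assumed ranges the bias is 0.01–0.30 points. The upper end would use all of the roughly 0.30 points of room under the ±1 rule, but it needs a 10% event rate, a 3-point shift, complete loss in one arm and complete retention in the other. At 2% and 2 points the chance of concluding equivalence is unchanged to the nearest percent. This should be fixed because it is cheap and because scores never collected cannot be recovered by analysis. Confidence is moderate.

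**What to change.** - **7.2:** allow replacement only when surgery is cancelled before the first incision and before any study injection, in either arm. Everyone whose operation starts stays in her randomised arm and is not replaced.
- **7.2 and the schedule of activities (1.3):** collect the 18–24 hour score, narcotic diary and day-14 inventory from everyone whose operation starts, whether or not she was injected.
- **9.3 and 9.4.2:** name ITT as the primary analysis set and mITT as supportive.
- **Reporting:** list replacements by arm with reasons.
- **7.1, 7.2 and 8.4.4:** reconcile what these sections say about discontinuation and withdrawal during surgery.

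The cost is one rewritten paragraph in 7.2 and matching wording elsewhere, with no new visits or staff. The drawback is that a few non-injected patients stay among the 128 and slightly dilute the contrast between timings.

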7.3 LOST TO FOLLOW-UP

A participant will be considered lost to follow-up if she fails to return for her scheduled visit and is unable to be contacted by the study site staff.

The following actions must be taken if a participant fails to return to the clinic for a required study visit:

- The site will attempt to contact the participant and reschedule the missed visit within one week and counsel the participant on the importance of maintaining the assigned visit schedule and ascertain if the participant wishes to and/or should continue in the study.
- Before a participant is deemed lost to follow-up, the investigator or designee will make every effort to regain contact with the participant (where possible, three telephone calls and, if necessary, a certified letter to the participant's last known mailing address or local equivalent methods). These contact attempts should be documented in the participant's medical record or study file.
- Should the participant continue to be unreachable, she will be considered to have withdrawn from the study with a primary reason of loss to follow-up.

8 STUDY ASSESSMENTS AND PROCEDURES

8.1 EFFICACY ASSESSMENTS

Efficacy will be assessed by regular discussions with the primary surgeon by email and by phone call. We will discuss which patients have consented to the study on a weekly basis and then discussions will be had on the morning of each procedure to determine which arm the patient has been randomized into. We will be having regular weekly meetings to ensure that the protocol is being followed and that the co-investigators are aware of which patients have already consented and which patients have agreed to the study over the phone but need to have consent done on the day of surgery. We have reviewed how injections will be given in the two groups during our monthly research meetings and will continue to review these at the monthly meetings. After the surgery is complete, efficacy will be again assessed to ensure that the patient received the local infiltration pending which arm the patient was randomized into by phone call or email with the co-investigator.

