2 INTRODUCTION

2.1 STUDY RATIONALE

Pelvic organ prolapse is becoming more common as women's life expectancy is increasing and the prevalence of obesity is rising. Many women undergo pelvic reconstructive surgery to treat their prolapse and improve their quality of life. The incidence of pelvic organ prolapse is 1.5-1.8 surgeries per 1,000 women years (1). Approximately 300,000 pelvic reconstructive surgeries are performed each year in the United States (1). There is a wide variety in surgical approaches and procedures for prolapse. One such procedure is a sacrocolpopexy in which the cervix or vaginal cuff is lifted to the anterior longitudinal ligament overlying the sacrum via a mesh graft. This can be done in a minimally invasive fashion with a laparoscopic or robotic approach or in an open abdominal approach. Numerous studies have shown this procedure to have a high success rate and long-term durability (2). As robotic/laparoscopic approach to surgery has shown shorter hospital-stays and improved patient outcomes, the robotic-assisted sacrocolpopexy has been rapidly incorporated into clinical practice (2).

In general, surgery causes a release of painful chemical mediators which has led to increased narcotic use, increased narcotic addiction, and number of pills prescribed. Most individuals who undergo surgery will require narcotics postoperatively to control their pain and some individuals have to extend their hospital stay until adequate pain control is achieved. Our study is aimed to reduce narcotic use, decrease hospital stay due to pain issues and determine if timing of adjunct pain medication improves pain scales for patients.

As postoperative pain after minimally invasive surgery is complex, specialists suggest that the effective analgesic treatment should be a multimodal approach (4). Use of local anesthetic with bupivacaine at robotic/laparoscopic trocar sites is the standard of care, however, there is no standard as to optimal timing that is most beneficial for patients to decrease pain. Currently, bupivacaine is used by providers at the trocar sites at either the beginning of the case or at the end of the case. From clinical

observation, it appears that postoperative pain levels reported from patients receiving either at the beginning of surgery (pre-) or end (post-incision) of the surgery are similar. This study aims to examine the difference in POD1 pain levels reported by patients between the two infiltration methods.

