 - Postoperative pain medication will be ordered for each patient as per standard enhanced recovery protocol
 - On Postoperative Day 1, the patient will be asked her pain scale on the Likert-pain scale. The Likert-pain scale is a 0-10 discrete integer scale. The investigators will check for patient's pain medication use before questionnaire administration. If a patient has received postoperative pain medication, the questionnaire will be administered at least 1.5 hours after the patient has received the pain medication.
 - Discharge medications will be ordered for each patient as per standard enhanced recovery protocol
 - The Brief Pain Inventory Questionnaire will be given to the patient at the 2 -week postoperative visit to be filled out and collected at the postoperative visit.
 - The Narcotic diary (in which the patient writes down how many narcotic tablets they have used per day since the surgery (provided and additional included) will be collected at the postoperative visit.

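### Nothing in the plan keeps the person who times or asks for the POD1 pain score unaware of the arm, and the equivalence rule leaves little room for even a small shift

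*Combined protocol and SAP*

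**What the plan says.** Section 4.1 describes a "Randomized, controlled, single-blinded study". Section 6.3, which covers measures against bias, lists "Patient-blinded study" and adds: "The surgeon at the time of intervention will not be blinded as to which arm the patient belongs". It says nothing about the person who obtains the pain score.

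Allocation travels by several routes:
- Section 4.1: "Surgeons will be notified by e-mail of their patient allocation on day of surgery".
- Section 6.2.1: "Study intervention will be emailed to investigator before surgery".
- Section 8.1: "discussions will be had on the morning of each procedure to determine which arm the patient has been randomized into". After the operation, delivery according to arm is checked again with the co-investigator by phone or e-mail.
- Section 6.1.2: the anesthesia team is told when the drug is being injected, which in practice reveals the arm to them.

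The primary outcome is one integer from 0 to 10 (section 9.1), obtained 18 to 24 hours after surgery (section 1.2). Section 4.1 says the patient is asked for it. It makes the investigators responsible for checking the patient's "pain medication use before questionnaire administration" and requires at least 1.5 hours after any dose, with no upper limit. It does not name the person who asks.

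Two other places bear on the fix. Section 6.4 describes a patient log with a daily pain score as well as tablet counts, whereas sections 1.2 and 4.1 describe the diary as tablets only. The risk assessment in section 8.4.4 describes POD1 safety contact as a phone call.

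**The concern.** The outcome is subjective and measured once. Someone who knows the arm could influence it in two ways: by how the question is put and recorded, and by the moment chosen within a 6-hour window under a rule that sets only a minimum interval after analgesia.

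Section 2.1 also records a prior view. The passage beginning "it appears that postoperative pain levels reported from patients receiving either at the beginning of surgery" goes on to say that levels look similar whichever timing is used. That expectation could draw the arms together. Other expectations could push them apart, and the documents do not settle the direction.

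The primary conclusion is at stake. Section 9.4.2 declares equivalence if the 95% CI lies within ±1 point, and a small arm-related shift moves the probability of that conclusion appreciably.

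**Working it through.** **Inputs (sections 9.2 and 9.4.2).** Difference 1 point, SD 2, two-sided alpha 0.05, power 0.80, 1:1 allocation, no drop-out, 64 per arm, equivalence margin ±1 judged by a 95% CI.

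**Reproducing the plan's figure.** Normal approximation: n = 2 × (1.960 + 0.842)² × 2² / 1² = 62.8, so 63 per arm. With the exact t test, power is 0.795 at 63 and 0.801 at 64, so the stated 64 per arm is confirmed.

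**Room left by the equivalence rule.**
- SE = 2 × √(2/64) = 0.354
- t(0.975, 126 df) = 1.979
- Half-width = 1.979 × 0.354 = 0.700
- Largest observed difference that still gives equivalence = 1 − 0.700 = 0.300

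**Effect of a shift.** The documents give no size for assessor influence, so the shift b is an assumption. Treating the SD as fixed at 2, P(equivalence) = Φ((0.300 − m)/0.354) − Φ((−0.300 − m)/0.354), where m is the mean difference after the shift.
- m = 1.00 (true difference 1, no shift): 2.4%
- m = 0.75 (shrunk by 0.25): 10.0%
- m = 0.50 (shrunk by 0.5): 27.4%
- m = 0.25 (true difference 0, shifted by 0.25): 49.7%
- m = 0 (true difference 0, no shift): 60.4%

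Allowing for estimation of the SD (2,000,000 simulated trials for the equivalence columns, noncentral t for the t-test columns) gives nearly the same answers:

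| Assumed shift b | True difference 1, shrunk by b: false equivalence | True difference 1, shrunk by b: t-test power | True difference 0, shifted by b: equivalence shown | True difference 0, shifted by b: significant t test |
|---|---|---|---|---|
| 0 | 2.5% | 80% | 60% | 5% |
| 0.1 | 4.6% | 71% | 58% | 5.9% |
| 0.2 | 8.0% | 61% | 53% | 8.7% |
| 0.25 | 10.3% | 56% | 50% | 10.8% |
| 0.3 | 12.9% | 50% | 46% | 13.4% |
| 0.5 | 27.7% | 29% | 28% | 28.9% |

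**The case against.** The strongest reply is that the patient rates her own pain and does not know her arm, while the 18-24 hour window and the 1.5-hour minimum already constrain timing. This stands in part: it removes the patient's own knowledge as a source of bias and narrows what an unblinded person could do. It does not settle who asks, or who picks the moment.

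The shifts above are assumed, and 0.5 is half the equivalence margin. That objection also stands. The table shows how sensitive the rule is, not how large any bias will be. An expectation that the timings are similar gives no arm-specific direction, so shrinkage towards zero is one scenario among several. The 60% chance of showing equivalence with no shift is a matter of sample size and is not evidence for this point.

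A reader might infer several stronger things that the documents do not support:
- *The whole team knows each arm.* The text names surgeons, the investigator, the co-investigator and an unspecified group holding the discussions. It does not say that every investigator is told.
- *Unblinded investigators do collect the score.* Only the analgesic check is assigned to investigators. Section 10.1.9.1 gives data collection generally to a medical monitor at the site, but that role is not described as unaware of allocation either.
- *The weekly meetings disclose allocations.* Section 8.1 gives them over to consent and adherence. Randomization is on the day of surgery, so they could not reveal the arms of upcoming cases.
- *Self-completion would eliminate the problem.* It removes prompting and recording by staff, but not their choice of when to hand over the form.

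**Conclusion.** The point holds as an open, inexpensively reducible risk to the primary outcome. The plan blinds the patient alone, circulates the arm before and after surgery among people who may include the score collector, and has no rule that keeps those roles apart. No bias has been shown.

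The half-width of 0.70 and the 0.30 limit follow from the plan's own 64 per arm and SD 2. If, by assumption, knowledge of the arm shrank a true 1-point difference by 0.25, false equivalence would be about four times as likely (10% against 2.4%). A shift of 0.1 would have a much smaller effect. The change is worth making because it costs little, not because a large bias is expected.

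**What to change.** - **Sections 4.1 and 6.3:** state that the patient writes down her own POD1 0-10 score, or that existing staff who were not told the allocation obtain it. A timed line in the diary would serve. Section 6.4 already places a daily pain score in the patient log, and the tablets-only descriptions in 1.2 and 4.1 should be reconciled with it. Where POD1 contact is by phone, she completes the line before the call.
- **Timing:** prespecify when within the existing 18-24 hour window the score is prompted, leaving the 1.5-hour condition as it is, so that unblinded staff do not choose the moment. Record the clock times of the score and of the last analgesic dose. Recording alone documents the choice but does not prevent it.
- **Section 8.1:** limit the morning-of-surgery and after-surgery exchanges about the arm to those who deliver, need to know of, or verify the injection, including the anesthesia team, and keep those people from collecting the POD1 score.

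**Cost:** a short form or diary line that must be completed within the window, and a shorter distribution list. The sample size stays at 64 per arm, and no additional staff are needed if the patient records the score or ward staff already present obtain it. The documents give no cost figures. Some risk remains, since staff who know the arm could still reveal it to the patient.
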